### 14.2.4.2 Time to Improvement on NIAID 8-Point Clinical Progression Outcomes Scale

*Use TTR Layout*

### 14.2.4.3 Figure of Improvement Proportion on NIAID 8-Point Clinical Progression Outcomes Scale (Best Case Scenario)

### 14.2.4.4 Figure of Improvement Proportion on NIAID 8-Point Clinical Progression Outcomes Scale (Worst Case Scenario)

*Use TTR Figure Layout*

## 14.2.5 EQ-5D-5L

### 14.2.5.1 EQ-5D-5L

Population: Intent-to-Treat Population / Per-Protocol Population

Characteristics	Treatment Group	Difference	P-value
--Repeat Population: <See populations above>			

. Repeat Visit:

Visit 2 (Day 1), Visit 4 (Day 8), Visit 6 (Day 14, EOT), Visit 7 (Day 28, F1), LOCF

. Repeat Variable:

*Total score of Q1~Q5, Imaginable Health Status*

N (Missing)	XXX (XXX)	TW (Visit 2 (Day 1)) 0.XXXX
Mean (SD)	XXX (XXX)	
Median (IQR)	XXX (XXX)	
Q1~Q3	XXX~XXX	
Min~Max	XXX~XXX	

*For Imaginable Health Status only*

≥ 90	XXX (XXX.X%)
< 90	XXX (XXX.X%)

Repeat [Visit - Visit 2 (Day 1)] except Visit 2 (Day 1)

N (Missing)	XXX (XXX)	TW 0.XXXX
N (Missing)	XXX (XXX)	
Mean (SD)	XXX (XXX)	
Median (IQR)	XXX (XXX)	
Q1~Q3	XXX~XXX	
Min~Max	XXX~XXX	

For W, normality is not applied

Groups Diff	§C - §S
Median (Asymptotic SE)	XXX
95% CI (HL)	XXX~XXX

For T, normality is applied

Groups Diff	§C - §S
Mean (SD)	XXX (XXX)
95% CI	XXX~XXX

Q1. Mobility, Q2. Self-Care, Q3. Usual Activities, Q4. Pain/Discomfort, Q5. Anxiety/Depression

### 14.2.5.2 Time to Improvement on EQ-5D-5L Imaginable Health Status

*Use TTR Layout*

### 14.2.5.3 Figure of Improvement Proportion on EQ-5D-5L Imaginable Health Status (Best Case Scenario)

### 14.2.5.4 Figure of Improvement Proportion on EQ-5D-5L Imaginable Health Status (Worst Case Scenario)

*Use TTR Figure Layout*

## 14.3 SAFETY DATA

### 14.3.1 Treatment Emergent Adverse Event – Subject Based Analyses

#### 14.3.1.1 Treatment Emergent AE – Summary

Population: Safety Population

Characteristics [Event#:Subj#]	Treatment Group
(Multi-Selection)	
N	XXX
Subjects with AE	XXX : XXX (XXX.X%)
~ Grade $\geq 3$	XXX : XXX (XXX.X%)
~ Grade 4	XXX : XXX (XXX.X%)
~ Grade 5	XXX : XXX (XXX.X%)
Subjects with Treatment-Related AE	XXX : XXX (XXX.X%)
~ Grade $\geq 3$	XXX : XXX (XXX.X%)
~ Grade 4	XXX : XXX (XXX.X%)
~ Grade 5	XXX : XXX (XXX.X%)
Subjects with AE Leading to Action Taken	XXX : XXX (XXX.X%)
~ Dose Reduced	XXX : XXX (XXX.X%)
~ Drug Interrupted	XXX : XXX (XXX.X%)
~ Drug Withdrawn by Subject	XXX : XXX (XXX.X%)
~ Drug Withdrawn Instructed by Investigator	XXX : XXX (XXX.X%)
Subjects with SAE	XXX : XXX (XXX.X%)
~ Requires or Prolongs Hospitalization	XXX : XXX (XXX.X%)
~ Life-Threatening SAE	XXX : XXX (XXX.X%)
~ Death SAE	XXX : XXX (XXX.X%)
~ SUSAR	XXX : XXX (XXX.X%)
~ Death SUSAR	XXX : XXX (XXX.X%)

Subject with multiple events are counted as one incidence.

Treatment Related is defined as Definitely Related, Probable Related, or Possibly Related

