1. PROTOCOL SUMMARY

1.1. SYNOPSIS

Title:	A Phase II, Randomized and Controlled Investigator-Initiated Trial Evaluating Safety, Pharmacokinetics and Clinical Benefit of Silmitasertib (CX-4945) in Outpatient Adult Subjects with Moderate Coronavirus Disease 2019 (COVID-19)	
Study Description:	
COVID-19 is characterized by SARS-CoV-2-induced upregulation of host protein kinase CK2 that catalyzes phosphorylation of many proteins, modulating their activities in cellular processes. SARS-CoV-2 nucleocapsid directly targets CK2 and this viral-host protein interaction affects many vital processes in host cells contributing to dysregulated host immune response, viral survival, replication and spread to nearby cells. CX-4945 demonstrated anti-viral and anti-inflammatory efficacy in COVID-19 in vitro studies and remarkable clinical benefits under emergency IND authorization. As CX-4945 is an inhibitor of the host protein kinase CK2, it does not impact on the effectiveness of other antiviral drugs or contribute to the emergence of viruses with reduced susceptibility to the drug.
 
This is a Phase II multicenter, open-label, randomized two-arm parallel-group controlled study in approximately 20 subjects to evaluate safety and explore putative clinical benefits of CX-4945 1000 mg BID dose in patients with moderate COVID-19. It will be a two-arm trial comparing the SOC/supportive care alone to the SOC/supportive care in combination with CX-4945(allocation ratio 1:1).
	
Primary Objective and Endpoints:	Primary Objective	Primary Endpoint
	To assess safety and tolerability of CX-4945 administered orally twice daily to patients with moderate COVID-19	Adverse events occurring from randomization (Day 1) to Day 60 (including vital signs, physical findings, clinical laboratory, and ECG results) as characterized by type, frequency, severity [as graded by Toxicity Grading Scale for Healthy Adult and Adolescent Volunteers Enrolled in Preventive Vaccine Clinical Trials (https://www.fda.gov/media/73679/download)], timing, seriousness, and relationship to study therapy.
Secondary Objectives and Endpoints:	Secondary Objectives	Secondary Endpoints
	To compare time to normalization of COVID-19-related	Number of days from Randomization (Day1) to the day when the following clinical signs are back to normal (as evaluated at every visit during the treatment period (Day

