3. STUDY OBJECTIVES AND ENDPOINTS

Primary Objective	Primary Endpoint
To assess safety and tolerability of CX-4945 administered orally BID to patients with moderate COVID-19	
Adverse events occurring from randomization (Day 1) to Day 60 (including vital signs, physical findings, clinical laboratory, and ECG results) as characterized by type, frequency, severity [(as graded by Toxicity Grading Scale for Healthy Adult and Adolescent Volunteers Enrolled in Preventive Vaccine Clinical Trials (https://www.fda.gov/media/73679/download)], timing, seriousness, and relationship to study therapy.
Secondary Objectives	Secondary Endpoints
To compare time to normalization of COVID-19-related clinical signs in CX-4945 treatment arm versus the control arm.	
Number of days from Randomization (Day1) to the day when the following clinical signs are back to normal as evaluated at every visit during the treatment period (Day 1, Day 4, Day 8, Day 11 and Day 14) and at Follow-up visits on Day 28 and Day 45 :
 
Fever is $\leq 36.6^{\circ}\text{C}$ from axillary site, or $< 37.2^{\circ}\text{C}$ from oral site or $< 37.8^{\circ}\text{C}$ from rectal or tympanic site)Respiratory rate is < 20 bpm while breathing room air at sea level$\text{SPO} \geq 96\%$ in room air without shortness of breath or dyspneaHeart rate < 90 beats per minute 
Note: If some signs listed above were caused by other conditions documented in the medical history and started before COVID-19, the patient can be considered as recovered, when these signs return to the previous (pre-COVID-19) values.

To compare duration of COVID-19-Related clinical symptoms in CX-4945 treatment arm versus the control arm.	Number of days from Randomization (Day1) to the day when: 
No key COVID-19-related symptoms scored higher than 1 as documented using a Patient Reported Outcome (PRO) instrument (a Patient Diary for Assessment of Common COVID-19-Related Symptoms – see Appendix 3),

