9.7.1. Analysis Populations

9.7.1.1. Intent-to-Treat (ITT)Population

The **ITT population** is defined as all randomized patients. This population will be used as the primary analysis population for analysis of the primary and secondary efficacy endpoints.

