9.8.4.2. Supportive Analysis

To assess the consistency of the primary analysis results, supportive analysis will be conducted using the ITT and PP populations. Statistical methodology for the supportive analyses will be the same as that of the primary analysis, with the exception of the analysis population used.

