### 1.4 Analysis Method

#### 1.4.1 Inferential Statistics

According to the protocol, no inferential statistics was planned. In the SAP, the inferential testing will be done as appropriate for treatment comparison.

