## 14 TABLES AND FIGURES

- *The texts in shaded Italic are for programming note.*
- *Column of Study Site includes columns of {001-CARE, 002-CAR, Total}*
- *Column of Treatment Group includes columns of {CX-4945, SOC, Total}*
- *Column 'Difference' denotes pairwise comparison statistics.*
- *Multi-Selection means 'A subject may be counted in more than one category'*
- *Description in <...> will be presented according to data values.*
- *For column p-value: refer to Abbreviations of statistics in [Instructions and Abbreviations] above.*
- *For Groups Diff., §C = CX-4945, §S = SOC,*  
*T denotes two sample t test, W denotes Wilcox\_t (Wilcoxon rank-sum test in t approximation),*  
*C denotes Chi-Square test, F denotes Fisher's exact test*

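### Adverse-event incidence, the core of the only primary endpoint, is tabulated by arm with no between-arm difference or interval

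*SAP*

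**What the plan says.** The primary objective (protocol 1.1) is "To assess safety and tolerability of CX-4945 administered orally twice daily to patients with moderate COVID-19". The primary endpoint is "Adverse events occurring from randomization (Day 1) to Day 60 (including vital signs, physical findings, clinical laboratory, and ECG results"), characterised by type, frequency, severity, timing, seriousness and relationship. Neither names a summary measure or a contrast between arms.

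Protocol 9.8.4 plans description only, and 9.8.4.3 asks for TEAE summaries by treatment group, including by causality and by impact on study treatment. SAP 1.4.1 then departs from the descriptive plan: "In the SAP, the inferential testing will be done as appropriate for treatment comparison". 

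The SAP table shells apply this unevenly:

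- **AE tables (14.3.1.1 to 14.3.1.8, Safety population).** Events, subjects and percentages, in rows such as "Subjects with Treatment-Related AE", under the treatment-group columns only. SAP section 14 defines that block: "Column of Treatment Group includes columns of {CX-4945, SOC, Total". There is no Difference, interval or p-value.
- **Viral clearance and load (14.2.3.1), EQ-5D-5L (14.2.5.1).** Group differences with 95% intervals, and p-values.
- **Continuous laboratory tests (LB Layout 1) and vital signs (14.3.8).** Group differences with 95% intervals, and ANCOVA or Wilcoxon p-values for change from baseline.
- **Physical examination (14.3.7) and ECG (14.3.9).** No comparison.

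Two protocol sentences use the word primary in connection with efficacy. Section 9.7.1.1 says of the ITT set: "This population will be used as the primary analysis population for analysis of the primary and secondary efficacy endpoints". Section 9.8.4.2 says: "To assess the consistency of the primary analysis results, supportive analysis will be conducted using the ITT and PP populations". The protocol defines no primary efficacy endpoint.

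**The concern.** Patients with COVID-19 will have events from the illness itself. The randomised control arm is what allows drug toxicity to be separated from that background, and the separation rests on the difference between arms. For the primary endpoint the reader gets two percentages side by side, while several secondary outcomes get an estimated difference and its interval.

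With about 10 patients per arm, two similar percentages can easily be read as evidence of no excess harm when they show very little. A visible gap can be over-read in the same way.

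A narrower problem concerns rows that do not mean the same thing in both arms. Dose reduced, drug interrupted and drug withdrawn describe actions on a study drug that Arm B does not receive (protocol 6.1.1; 0 mg in Table 2). The treatment-related rows depend on causality judged by an investigator who knows the allocation. A Total column across both arms has no clear meaning for either set.

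**Working it through.** **Inputs.** Protocol 9.3 gives approximately 20 subjects randomised 1:1 and no power calculation, so there is no stated figure to reproduce. I assume exactly 10 per arm. The documents give no expected AE rates, so the counts below are illustrative and span a range.

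**One arm.** For 0 events in 10, the exact two-sided 95% upper limit is 1 - 0.025^(1/10) = 0.308, or 31%.

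**Difference between arms (Newcombe).** The Wilson limits for x/n, with p = x/n and z = 1.96, are

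[p + z²/(2n) ± z·√(p(1-p)/n + z²/(4n²))] / (1 + z²/n).

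With d = p1 - p2, the interval runs from d - √[(p1-l1)² + (u2-p2)²] to d + √[(u1-p1)² + (p2-l2)²].

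*0/10 v 0/10.* The Wilson upper limit is 0.384/1.384 = 0.278 and the lower limit is 0. The interval is 0 ± 0.278, or -28 to +28 points.

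*4/10 v 1/10.* The Wilson limits are 0.1682 to 0.6873 and 0.0179 to 0.4041.
- Lower: 0.300 - √(0.2318² + 0.3041²) = 0.300 - 0.382 = -0.082.
- Upper: 0.300 + √(0.2873² + 0.0821²) = 0.300 + 0.299 = 0.599.

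| CX-4945 v SOC | Difference (points) | Newcombe 95% interval |
|---|---|---|
| 0/10 v 0/10 | 0 | -28 to +28 |
| 2/10 v 0/10 | +20 | -11 to +51 |
| 4/10 v 1/10 | +30 | -8 to +60 |
| 5/10 v 2/10 | +30 | -11 to +60 |
| 7/10 v 3/10 | +40 | -3 to +67 |

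**Why not reuse the interval in SAP 14.2.3.1.** That table uses the normal approximation. At 0/10 v 0/10 its standard error is √(0×1/10 + 0×1/10) = 0. The interval would have zero width and would state certainty where the data give least.

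**Why an interval and not a test.** At 10 per arm, a two-sided Fisher p of 0.05 or less needs at least 5 v 0, 7 v 1, 8 v 2 or 9 v 3. Power is 12% for true rates of 60% v 30% and 24% for 70% v 30%. A non-significant p-value would add little and could be misread as reassurance.

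**Total column.** If 4 of 10 CX-4945 patients had a dose interruption, the arm rate is 4/10 = 40%. Under Total it becomes 4/20 = 20%, because the denominator includes 10 patients with no study drug to interrupt.

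**The case against.** The strongest reply is that the AE tables do what the protocol asks. The primary objective says assess, whereas a secondary objective reads "To compare duration of COVID-19-Related clinical symptoms in CX-4945 treatment arm versus the control arm". Protocol 9.8.4 plans no inferential statistics, 9.3 calls the study proof-of-concept, and 9.8.4.3 asks only for summaries by arm. This stands: leaving AE incidence untested is consistent with the protocol and ordinary at this size. It does not justify leaving out the uncertainty, since the SAP has already moved past pure description for other outcomes. SAP 1.4.4 has a general Fisher or chi-square rule for categorical data, but the AE shells do not carry it.

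Stronger readings that a reader might infer are not supported:

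- **The primary endpoint is never compared between arms.** Its laboratory and vital-sign components are compared, by ANCOVA, Wilcoxon or categorical tests (SAP 1.4.3, 14.3.2 to 14.3.6, 14.3.8). The gap addressed here is AE incidence.
- **Only raw counts are shown.** Percentages with denominators are given, so a reader could compute the difference and interval by hand.
- **Any efficacy endpoint could become the primary analysis.** The wording in protocol 9.7.1.1, 9.7.1.2 and 9.8.4.2 is loose, and SAP 1.2 reprints part of it. It changes no output: the efficacy shells already run in ITT and PP, and the AE shells in the Safety population.
- **The treatment-related rows should be removed from the SOC arm.** Protocol 9.8.4.3 requires causality by treatment group, relationship is part of the primary endpoint, and control patients may receive active agents such as remdesivir (protocol 4.1), so an event can be judged related there. The rows are poorly comparable, but they are not void.

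It can also be said that the Total column is cosmetic because the arm-specific figure sits beside it. That is fair as to size, but the Total percentage still has a misleading denominator.

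**Conclusion.** The point holds for AE incidence. The core of the only primary endpoint is presented without a between-arm difference or a measure of its uncertainty, while several other outcomes in the same SAP have both. At an assumed 10 per arm, the interval spans about 56 points at 0 v 0 (2 × 27.8) and 68 points at 4 v 1 (59.9 + 8.2). The percentages alone do not convey this. The widths depend on the assumed arm size and illustrative counts, but every row of the table above includes zero and extends to differences of 28 points or more.

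The study-drug action rows do not apply to Arm B, so their Total percentage is misleading. The treatment-related rows are affected by open-label attribution. The documents give no attribution rates, so I put no size on that effect. The loose use of primary for efficacy is a minor wording fault.

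**What to change.** 1. In SAP 14.3.1.1, add a Difference column (CX-4945 minus SOC) with a Newcombe or exact 95% interval and no p-value, in the Safety population, for three all-cause rows: any TEAE, Grade 3 or higher TEAE, and SAE. Do not use the normal approximation from 14.2.3.1.
2. In 14.3.1.1 and 14.3.1.6, show the study-drug action rows with the CX-4945 denominator only and no Total. Marking the SOC column not applicable keeps the by-arm layout of protocol 9.8.4.3. SAP 14.1.9 already uses a CX-4945-only column.
3. Keep the treatment-related rows by arm, as 9.8.4.3 requires. Drop the Total and footnote that open-label attribution makes them not comparable across arms.
4. In SAP section 1, state that the word primary in protocol 9.7.1.1, 9.7.1.2 and 9.8.4.2 refers to no efficacy endpoint.

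The cost is a short SAP paragraph, one extra column and some footnotes. No new data and no change to trial conduct are needed. The downside is that wide intervals will make the safety conclusion look less certain, which is an accurate picture at this sample size.

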#### 14.3.1.2 Treatment Emergent AE – Subjects with AE

#### 14.3.1.3 Treatment Emergent AE – Subjects with Treatment-Related AE

Population: Safety Population

Characteristics	Treatment Group
(Multi-Selection by XXX, System Organ Class and Preferred Term)	
N	XXX
At least one below [Event#:Subj#]	XXX : XXX (XXX.X%)
~ <MedDRA Body System1>	XXX : XXX (XXX.X%)
~ <MedDRA Preferred Term 1>	XXX : XXX (XXX.X%)
~ <MedDRA Preferred Term 2>	XXX : XXX (XXX.X%)
~ <MedDRA Preferred Term 3>	XXX : XXX (XXX.X%)
~ <MedDRA Body System2>	XXX : XXX (XXX.X%)
~ <MedDRA Preferred Term 1>	XXX : XXX (XXX.X%)
~ <MedDRA Preferred Term 2>	XXX : XXX (XXX.X%)
~ <MedDRA Preferred Term 3>	XXX : XXX (XXX.X%)

For each MedDRA (version 23.1) SOC or Preferred Term, subject with multiple events are counted as one incidence.

[For 14.3.1.3] Treatment Related is defined as Definitely Related, Probable Related, or Possibly Related

**14.3.1.4 Treatment Emergent AE – Subjects with Grade  $\geq 3$  AE**
**14.3.1.5 Treatment Emergent AE – Subjects with Grade  $\geq 3$  Treatment-Related AE**

Population: Safety Population

Characteristics	Treatment Group
(Multi-Selection by Severity Grade, System Organ Class and Preferred Term)	
N	XXX
At least one below [Event#:Subj#]	XXX : XXX (XXX.X%)
~ Repeat Severity Grade:	
Grade $\geq 3$ , Grade 4, Grade 5	XXX : XXX (XXX.X%)
~ <MedDRA Body System1>	XXX : XXX (XXX.X%)
~ <MedDRA Preferred Term 1>	XXX : XXX (XXX.X%)
~ <MedDRA Preferred Term 2>	XXX : XXX (XXX.X%)
~ <MedDRA Preferred Term 3>	XXX : XXX (XXX.X%)
~ <MedDRA Body System2>	XXX : XXX (XXX.X%)
~ <MedDRA Preferred Term 1>	XXX : XXX (XXX.X%)
~ <MedDRA Preferred Term 2>	XXX : XXX (XXX.X%)
~ <MedDRA Preferred Term 3>	XXX : XXX (XXX.X%)

*[For 14.3.1.5] Treatment Related is defined as Definitely Related, Probable Related, or Possibly Related*

**14.3.1.6 Treatment Emergent AE – Subjects with AE Leading to Action Taken**

Population: Safety Population

Characteristics	Treatment Group
(Multi-Selection by Action Taken, System Organ Class and Preferred Term)	
N	XXX
At least one below [Event#:Subj#]	XXX : XXX (XXX.X%)
~ Repeat Action Taken:	
Dose Increased, Dose Reduced, Drug Interrupted,	
Drug Withdrawn by Subject,	
Drug Withdrawn Instructed by Investigator	XXX : XXX (XXX.X%)
~ <MedDRA Body System1>	XXX : XXX (XXX.X%)
~ <MedDRA Preferred Term 1>	XXX : XXX (XXX.X%)
~ <MedDRA Preferred Term 2>	XXX : XXX (XXX.X%)
~ <MedDRA Preferred Term 3>	XXX : XXX (XXX.X%)
~ <MedDRA Body System2>	XXX : XXX (XXX.X%)
~ <MedDRA Preferred Term 1>	XXX : XXX (XXX.X%)
~ <MedDRA Preferred Term 2>	XXX : XXX (XXX.X%)
~ <MedDRA Preferred Term 3>	XXX : XXX (XXX.X%)

**14.3.1.7 Treatment Emergent AE – Subjects with Serious Adverse Event (SAE)**
**14.3.1.8 Treatment Emergent AE – Subjects with Suspected Unexpected Serious Adverse Reaction (SUSAR)**

*SUSAR: Unexpected Treatment Related SAE*

Population: Safety Population

Characteristics	Treatment Group
(Multi-Selection by SAE Criteria, System Organ Class and Preferred Term)	
N	XXX
At least one below [Event#:Subj#]	XXX : XXX (XXX.X%)
Repeat SAE Criterion:	
Any SAE Criterion, Requires or Prolongs Hospitalization, death, ...	XXX : XXX (XXX.X%)
~ <MedDRA Body System1>	XXX : XXX (XXX.X%)
~ <MedDRA Preferred Term 1>	XXX : XXX (XXX.X%)
~ <MedDRA Preferred Term 2>	XXX : XXX (XXX.X%)
~ <MedDRA Preferred Term 3>	XXX : XXX (XXX.X%)
~ <MedDRA Body System2>	XXX : XXX (XXX.X%)
~ <MedDRA Preferred Term 1>	XXX : XXX (XXX.X%)
~ <MedDRA Preferred Term 2>	XXX : XXX (XXX.X%)
~ <MedDRA Preferred Term 3>	XXX : XXX (XXX.X%)

SAE Criteria 'F/L/H' and 'F/L' will be counted as 'F' only, and 'L/H' as 'L', where F=Fatal (Death), L=Life threatening, H=Require hospitalization or prolongation of existing hospitalization.

### 14.3.2 Laboratory Examination – Hematology

- 14.3.2.1 Hematology – <Item 1 and Unit>
- 14.3.2.2 Hematology – <Item 2 and Unit>
- 14.3.2.3 .... Refer to [Instructions and Abbreviations] of section 16 for the test terms

### 14.3.3 Laboratory Examination – Chemistry

- 14.3.3.1 Chemistry – <Item 1 and Unit>
- 14.3.3.2 Chemistry – <Item 2 and Unit>
- 14.3.3.3 .... Refer to [Instructions and Abbreviations] of section 16 for the test terms

### 14.3.4 Laboratory Examination – Inflammatory Marker

- 14.3.4.1 Inflammatory Marker – <Item 1 and Unit>
- 14.3.4.2 Inflammatory Marker – <Item 2 and Unit>
- 14.3.4.3 .... Refer to [Instructions and Abbreviations] of section 16 for the test terms

### 14.3.5 Laboratory Examination – Coagulation

- 14.3.5.1 Coagulation – <Item 1 and Unit>
- 14.3.5.2 Coagulation – <Item 2 and Unit>
- 14.3.5.3 .... Refer to [Instructions and Abbreviations] of section 16 for the test terms

### 14.3.6 Laboratory Examination – Urinalysis

- 14.3.6.1 Urinalysis – <Item 1 and Unit>
- 14.3.6.2 Urinalysis – <Item 2 and Unit>
- 14.3.6.3 .... Refer to [Instructions and Abbreviations] of section 16 for the test terms

*<LB Layout 1: For Continuous Laboratory Test; Clinical relevance analyses will be excluded if not applicable>*

Population: Safety Population

Characteristics	Treatment Group	Difference	p-value
. Repeat Visit: No ‘Visit 1 (Screening)’ for IL-6: Visit 1 (Screening), Baseline, Adjusted Visit 3 (Day 4), Adjusted Visit 4 (Day 8), Adjusted Visit 5 (Day 11), Adjusted Visit 6 (Day 14, EOT), Visit 7 (Day 28, F1), Visit 8 (Day 45, F2)			
N (Missing)	XXX (XXX)		
Mean (SD)	XXX (XXX)		
Median (IQR)	XXX (XXX)		
Q1~Q3	XXX~XXX		
Min~Max	XXX~XXX		
		T/W <Baseline Only>	
		0.XXXX	

For W, normality is not applied <Baseline Only>

Groups Diff	§C - §S
Median (Asymptotic SE)	XXX
95% CI (HL)	XXX~XXX

Characteristics	Treatment Group	Difference	p-value
For T, normality is applied <Baseline Only>			
Groups Diff		§C - §S	
Mean (SD)		XXX (XXX)	
95% CI		XXX~XXX	
N (Missing)	XXX (XXX)		
Normal	XXX (XX.X%)		
NCS	XXX (XX.X%)		
CS (Medical History)	XXX (XX.X%)		
CS (Adverse Event)	XXX (XX.X%)		
. Repeat [Visit – Baseline] excluding Visit 1 (Screening) and Baseline			ANCOVA/W
N (Missing)	XXX (XXX)		0.XXXX
Mean (SD)	XXX (XXX)		
Median (IQR)	XXX (XXX)		
Q1~Q3	XXX~XXX		
Min~Max	XXX~XXX		
95% CI (WI)	XXX~XXXwt		
For W, normality is not applied			
Groups Diff		§C - §S	
95% CI (HL)		XXX~XXX	
For ANOVA, normality is applied	XXX (XXX)		
LsMean (SE)	XXX~XXX		
95% CI of LsMean			
Groups Diff. (T)		§C-§S	
Difference of LsMean		XXX	
95% CI of LsMean		XXX~XXX	
ANCOVA Model (p-value 0.XXXX) with effect Treatment (p-value 0.XXXX), Baseline (p-value 0.XXXX), Treatment*Baseline (p-value 0.XXXX).			
. Repeat [<Baseline> to <Visit>]			
N (Missing)	XXX (XXX)		
Relieved	XXX (XX.X%)		
Unchanged	XXX (XX.X%)		
Worsened (Medical History)	XXX (XX.X%)		
Worsened (Adverse Event)	XXX (XX.X%)		

For Item excluding IL-6 Baseline is Visit 2 (Day 1) data, or is Visit 1 if Visit 2 (Day 1) is null

For IL-6 Baseline is Visit 2 (Day 1) data

Refer to [Instructions and Abbreviations] of title pages for Transition of Clinical Relevance

**<LB Layout 2: For Categorical Urinalysis Test, including pH;  
 MHCHISQ for PH, C/F for else>**

Population: Safety Population

Characteristics	Treatment Group	p-value
. Repeat Visit: Visit 1 (Screening), Baseline, Adjusted Visit 3 (Day 4), Adjusted Visit 4 (Day 8), Adjusted Visit 5 (Day 11), Adjusted Visit 6 (Day 14, EOT), Visit 7 (Day 28, F1), Visit 8 (Day 45, F2)		MHCHISQ / C/F <Baseline Only> 0.XXXX
N (Missing)	XXX (XXX)	
<Value 1>	XXX (XX.X%)	
<Value 2>	XXX (XX.X%)	
<Value 3>	XXX (XX.X%)	
N (Missing)	XXX (XXX)	
Normal	XXX (XX.X%)	
NCS	XXX (XX.X%)	
CS (Medical History)	XXX (XX.X%)	
CS (Adverse Event)	XXX (XX.X%)	
. Repeat [<Visit> – <Baseline>] for pH Repeat [<Baseline> to <Visit>] for else For <Visit> excluding Visit 1 (Screening) and Baseline		MHCHISQ / C/F
N (Missing)	XXX (XXX)	0.XXXX
<Value 1>	XXX (XX.X%)	
<Value 2>	XXX (XX.X%)	
<Value 3>	XXX (XX.X%)	
. Repeat [<Baseline> to <Visit>]		
N (Missing)	XXX (XXX)	
Relieved	XXX (XX.X%)	
Unchanged	XXX (XX.X%)	
Worsened (Medical History)	XXX (XX.X%)	
Worsened (Adverse Event)	XXX (XX.X%)	

Baseline is Visit 2 (Day 1) data, or is Visit 1 if Visit 2 (Day 1) is null

Refer to [Instructions and Abbreviations] of title pages for Transition of Clinical Relevance

[For Color and Appearance] Data of normal values will be coded as ‘Normal’, and data not in normal values will be coded as ‘Abnormal’.

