### 1.4.3 Method for Continuous Data

Demographics, baseline characteristics and continuous efficacy data will be analyzed by using two sample t test or Wilcoxon rank-sum test as appropriate. Net changes from pre-treatment laboratory test results and vital signs will be analyzed by using ANCOVA model with baseline value as covariate or Wilcoxon rank-sum test as appropriate.

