### 3 Mock-up Tables and Figures

The Mock-up “TABLES and FIGURES” is planned according to ICH E3, in which relevant Clinical Study Report (CSR) section is 14. The words shadowed below are to be adjusted or repeated upon real data, or just for notification.

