**For CI and p-value (between groups):**

Wilcox\_t denotes Wilcoxon rank-sum test (Mann-Whitney U Test) in t approximation

Wilcox\_z denotes Wilcoxon rank-sum test (Mann-Whitney U Test) in z approximation

ANOVA denotes Treatment effect in ANOVA model

ANCOVA denotes Treatment effect in ANCOVA model

For 95% CI (HL), HL denotes CI using Hodges-Lehman for median

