### 14.3.8 Vital Signs, Body Weight and SpO2

- 14.3.8.1 Vital Signs – Temperature [degree C]
- 14.3.8.2 Vital Signs – Respiratory Rate [breaths/min]
- 14.3.8.3 Vital Signs – Systolic Blood Pressure [mmHg]
- 14.3.8.4 Vital Signs – Diastolic Blood Pressure [mmHg]
- 14.3.8.5 Vital Signs – Heart Rate [beats/min]
- 14.3.8.6 Vital Signs – Weight [kg]
- 14.3.8.7 Vital Signs – Pulse Oxygen Saturation (SpO2) [%]

Population: Safety Population		Treatment Group	p-value
Characteristics			
. Repeat Visit:			
Visit 1 (Screening), Baseline,			
Adjusted Visit 3 (Day 4), Adjusted Visit 4 (Day 8), Adjusted Visit 5 (Day 11),			
Adjusted Visit 6 (Day 14, EOT), Visit 7 (Day 28, F1), Visit 8 (Day 45, F2)			
N (Missing)	XXX (XXX)		
Mean (SD)	XXX (XXX)		
Median (IQR)	XXX (XXX)		
Q1~Q3	XXX~XXX		
Min~Max	XXX~XXX		
For W, normality is not applied		§C - §S	
Groups Diff			
Median (Asymptotic SE)	XXX		
95% CI (HL)	XXX~XXX		
For T, normality is applied		§C - §S	
Groups Diff			
Mean (SD)	XXX (XXX)		
95% CI	XXX~XXX		
For Temperature, Respiratory Rate, Heart Rate, Pulse Oxygen Saturation (SpO2)			
Normal	XXX (XXX.X%)	C/F	
Abnormal	XXX (XXX.X%)	0.XXXX	
. Repeat [Visit – Baseline] excluding Visit 1 (Screening) and Baseline			ANCOVA/W
N (Missing)	XXX (XXX)		0.XXXX
Mean (SD)	XXX (XXX)		
Median (IQR)	XXX (XXX)		
Q1~Q3	XXX~XXX		
Min~Max	XXX~XXX		
95% CI (WI)	XXX~XXXwt		
For W, normality is not applied		§C - §S	
Groups Diff			
95% CI (HL)	XXX~XXX		
For ANCOVA, normality is applied		XXX (XXX)	
		XXX~XXX	
LsMean (SE)			
95% CI of LsMean			
Groups Diff. (T)	§C- §S		
Difference of LsMean	XXX		
95% CI of LsMean	XXX~XXX		

ANCOVA Model (p-value 0.XXXX) with effect Treatment (p-value 0.XXXX), Baseline (p-value 0.XXXX), Treatment\*Baseline (p-value 0.XXXX).

Baseline is Visit 2 (Day 1) data, or is Visit 1 if Visit 2 (Day 1) is null

[Temperature] Normal: <36.6°C from axillary site, or < 37.2°C from oral site or < 37.8°C from rectal or tympanic site

[Respiratory Rate] Normal: < 20 breaths/min

[Heart Rate] Normal: <90 beats/min

[Pulse Oxygen Saturation (SpO2)] Normal: ≥ 96%

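### The ANCOVA in SAP 1.4.3 has baseline as a covariate, the table shells add a treatment-by-baseline interaction, and the SAP does not say which model gives the Treatment p-value

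*SAP*

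**What the plan says.** SAP 1.4.3 sets the method for changes in laboratory values and vital signs: an "ANCOVA model with baseline value as covariate", or a Wilcoxon test. It mentions no interaction.

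The shells read differently. LB Layout 1 is printed under SAP 14.3.6 and serves the continuous laboratory tests of 14.3.2 to 14.3.6. In its table body it has one ANCOVA line with a single overall model p-value, followed by "with effect Treatment (p-value 0.XXXX), Baseline (p-value 0.XXXX), Treatment*Baseline (p-value 0.XXXX". Section 14.3.8 puts the same line below its table: "ANCOVA Model (p-value 0.XXXX) with effect Treatment (p-value 0.XXXX), Baseline (p-value 0.XXXX", again followed by the interaction. LB Layout 1 also contains the rule "For IL-6 Baseline is Visit 2 (Day 1) data", so it covers the inflammatory markers. Protocol section 3 lists changes in those markers as a secondary endpoint.

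The abbreviations list, under "For CI and p-value (between groups", says "ANCOVA denotes Treatment effect in ANCOVA model" but does not give the model's terms. SAP 3.1 decides only when Wilcoxon replaces ANCOVA (Shapiro-Wilk p-value of 0.05 or less). No section centres baseline, names a type of sums of squares, or calls the interaction a check on equal slopes.

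**The concern.** A line with one overall model p-value and three effects reads most naturally as one fitted model that contains the interaction. In such a model the Treatment coefficient is not an overall treatment effect. With uncentred baseline it is the arm difference for a patient whose baseline value is zero, which has no meaning for temperature, heart rate or SpO2. The least-squares-mean difference and its interval, printed in the same table, are normally evaluated at the mean baseline. A reader could therefore see a p-value and an interval that point in different directions.

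The labels do not settle the matter. LB Layout 1 heads its least-squares-mean block ANOVA while its p-value column says ANCOVA/W; 14.3.8 says ANCOVA in both places.

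Up to 42 rows in 14.3.8 are exposed (7 variables × 6 post-baseline visits), and 24 for the inflammatory markers (6 markers × Days 4, 8, 11 and 14), less any that go to Wilcoxon.

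**Working it through.** The plan gives no power, effect size or variance, so there is no figure to reproduce. Protocol 9.3 gives about 20 patients randomized 1:1, hence n = 10 per arm. Everything else numerical below (means, SDs, correlations, effects, two-sided 0.05) is assumed.

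**The two models.** With T the arm indicator and x the baseline value:

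- Model 1 (1.4.3): change = a + τT + βx + e, with 20 − 3 = 17 residual degrees of freedom.
- Model 2 (shells): change = a + τT + βx + γTx + e, with 20 − 4 = 16.

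In Model 2 the arm difference at baseline x is τ + γx. The raw-baseline Type III test for Treatment tests τ alone, that is x = 0. The least-squares-mean difference at the mean baseline is τ + γx̄.

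**Loss of precision.** In Model 2, Var(τ̂) = σ²[2/n + x̄_A²/S_A + x̄_B²/S_B], where S is each arm's sum of squares of baseline about its mean. Put n = 10, S ≈ 9 SD² and r = baseline mean/SD. Then SE(τ̂) ≈ σ√(0.2 + 2r²/9). With outcome SD 1 and correlation 0.5, σ = √(1 − 0.25) = 0.866.

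- r = 0: 0.866 × √0.200 = 0.39
- r = 2: 0.866 × √1.089 = 0.90
- r = 5: 0.866 × √5.756 = 2.08
- r = 10: 0.866 × √22.42 = 4.10

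The SE in Model 1 stays at 0.39 throughout.

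**Simulation 1.** 4,000 trials per row, equal slopes, true difference 1.2 outcome SD (1.2/0.866 = 1.39 residual SD):

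| Baseline mean/SD | Median SE of τ̂, Model 2 | Model 1 rejects | Type III Treatment, Model 2, rejects | LS-mean difference, Model 2, rejects | Last two disagree |
|---|---|---|---|---|---|
| 0 | 0.40 | 82% | 79% | 82% | 5% |
| 2 | 0.94 | 80% | 23% | 80% | 59% |
| 5 | 2.2 | 80% | 8% | 80% | 73% |
| 10 | 4.3 | 80% | 7% | 80% | 75% |

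The simulated SEs follow the formula. With no effect and equal slopes, each test rejects in about 4-6% of trials. If the slopes differ by 0.5 but the arms do not differ at the mean baseline, the Type III Treatment test rejects in 17-19% of trials at ratios 2 to 10, against about 6% for the LS-mean difference.

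**Simulation 2.** 6,000 trials per cell, correlation 0.5, effects in residual SD. Entries are the share of trials in which exactly one of these occurs: the LS-mean interval excludes zero, or the Type III p-value is below 0.05.

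| Baseline mean/SD | 0 | 0.5 | 1.0 | 1.5 |
|---|---|---|---|---|
| 9.5 to 74 | 8-9% | 19-21% | 50-52% | 81-82% |
| 2 | 8% | 18% | 45% | 62% |
| 1 | 6% | 14% | 31% | 36% |
| 0.5 | 4% | 9% | 17% | 16% |

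At ratios of 9.5 or more, the Type III test rejects in 5-6% of trials at every effect size; Model 1 rejects in 5 / 17-18 / 53-54 / 86-87%. At 1.5 SD nearly all conflicts are an interval excluding zero beside a non-significant p-value. Correlations of 0.3 and 0.7 (ratio 9.5) give 8-9 / 20-21 / 51-52 / 80-82%.

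**Skewed markers.** For lognormal data with CV 0.5 / 1 / 2, the share of trials that pass Shapiro-Wilk (pooled change) and still conflict is 7 / 4 / 2% with no effect and 61 / 30 / 9% at 1.5 SD. Testing normality by arm gives 55 / 25 / 7% at 1.5 SD. The SAP does not say which data Shapiro-Wilk is applied to.

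**Other conventions.** A sequential (Type I) test with Treatment entered first leaves chance baseline imbalance in the numerator while the error term is baseline-adjusted. With no effect it rejects in 10.7%, 7.9% and 7.0% of trials at correlations 0.3, 0.5 and 0.7. Model 1 gives 4.8-5.0% and a Type II test 4.7-4.9%.

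**The case against.** The strongest reply is that this is under-specification and not a contradiction. A model with an interaction still has baseline as a covariate, so 1.4.3 does not strictly exclude it. The methods text should outrank a mock-up, and the abbreviations place p-value and interval under one heading and one treatment effect. Printing an interaction p-value as a slope check is common practice. SAP section 3 adds "The words shadowed below are to be adjusted or repeated upon real data, or just for notification", and the shading cannot be seen in the text available, so the line may be adjustable. These points show a leaning, but none names the model. The (T) tag on the LS-mean difference row does not help: section 14 says "T denotes two sample t test", which is neither model.

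Second, the large conflict rates need four choices that the SAP does not make: interaction kept, raw baseline, Type III test, and LS means at the mean baseline. They also need large true effects. This stands, and the result is conditional on it.

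Third, the normal-data rates leave out the Shapiro-Wilk switch. Applying it to continuous normal data lowers the 1.5 SD figure only to 78-79%. For coarsely recorded variables the effect is larger. If the SD is about one recording unit (assumed, mean/SD 46), 45-63% of trials go to Wilcoxon, and ANCOVA conflicts fall from 8.6% to 2.9% with no effect, 47% to 22% at 1.0 SD and 78% to 46% at 1.5 SD. The upper figures may therefore be too high for such variables.

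Fourth, the row counts are upper limits. The vital signs in the protocol's schedule omit weight, recovered patients may have Day 28 and Day 45 visits by phone, and the SAP's list of marker terms sits in a section not available here.

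**Conclusion.** The concern holds, as a minor point. The methods text and the shells describe different models, and the SAP does not say which one produces the Treatment p-value. Followed as written, with raw baseline and a partial test, the shells give a p-value with almost no power wherever the baseline mean is large relative to its SD, beside an interval that keeps its power. If the interaction is only a separate check, there is no conflict.

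The consequence is limited. Protocol 9.3 states that the sample size has no power basis, the adverse-event tables carry no p-values, the LS-mean interval remains usable, and no decision rule uses these tests. The absence of a named model is certain; the size of the harm depends on the assumed inputs and software conventions above. It still deserves correction, because SAP 1.4.1 adds inferential testing that the protocol did not plan, and the inflammatory markers are a secondary endpoint.

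**What to change.** Add one sentence to SAP 1.4.3: the Treatment p-value, the least-squares-mean difference and its confidence interval all come from the model with Treatment and Baseline only. If the interaction is wanted, report its p-value from a separate model labelled as an equal-slopes check that does not feed the treatment comparison. Change the ANCOVA lines in LB Layout 1 and 14.3.8 to match, and correct the ANOVA label in LB Layout 1 at the same time.

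The cost is one sentence and two shell lines. No new data are needed, and the reported model gains one residual degree of freedom (17 instead of 16 at 10 per arm).
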